## 5.2.5. Management of Toxicity Related to Seribantumab

In the event that a patient experiences a toxicity  $\geq$  Grade 3 that is not an IRR and is possibly, probably or definitively related to seribantumab treatment, and not related to fulvestrant, it is at the investigator's discretion to hold dosing or discontinue treatment with seribantumab. Prior to holding the dose or discontinuing treatment, the investigator must notify the sponsor and Medical Monitor.

In the event that seribantumab treatment has been held for 28 consecutive days, the patient should be discontinued. No dose reductions for seribantumab are permitted.

# 5.2.5.1. Potential Toxicities with the Combination of Seribantumab and Fulvestrant

In addition to the established toxicities of fulvestrant, it is expected that the addition of seribantumab to fulvestrant may lead to an increased frequency of low grade diarrhea, rash, alopecia, stomatitis, hypokalemia and hypomagnesaemia. A slight increase in grade 3 diarrhea and/or hypokalemia may be observed, as well, in the combination setting. In previous studies, these events were generally well controlled with symptomatic treatments per institutional standards.

Pulmonary embolisms, which exist as an identified risk for chemotherapies (Karavasilis et al., 2014; Kellokumpu-Lehtinen et al., 2012; Matulonis et al., 2008; Reck et al., 2014) have also been described as an adverse event of special interest (AESI) for ErbB-pathway related inhibitors, including seribantumab when administered in combination with paclitaxel. Increased frequencies were observed in combination of seribantumab with paclitaxel in two completed randomized studies in neo-adjuvant breast cancer (4 (3.1%) on the treatment arm vs. 0 (0%) on the control arm) and platinum-resistant ovarian cancer (6 (4.3%) on the treatment arm vs. 1 (1.3%) on the control arm). There was no general increase in venous thromboembolic events reported for these two studies. Pulmonary embolisms may be observed at a higher frequency with the combination of seribantumab and endocrine therapies. No increases in the frequency of pulmonary embolisms or other venous thromboembolic complications were observed in randomized studies with seribantumab in combination with exemestane in metastatic breast cancer.

Patients who have experienced a venous thromboembolic event within 60 days of signing the main consent form for this study should have been treated with anti-coagulants for at least 7 days prior to beginning treatment and for the duration of treatment on this study.

#### 5.3. Fulvestrant

Fulvestrant (trade name: Faslodex®) is an estrogen receptor (ER) antagonist that binds to the estrogen receptor in order to downregulate the ER protein in human breast cancer cells.

For managing patients receiving fulvestrant, investigators can use institutional guidelines, the fulvestrant package insert, or the following, which has been obtained from the Falslodex® US package insert (AstraZeneca, 2012).

## 5.3.1. Fulvestrant Formulation, Packaging, Labeling, and Storage

Please refer to the fulvestrant package insert located in the pharmacy binder for specific information on the fulvestrant formulation.

Fulvestrant will be supplied by the Sponsor and labeled for investigational use only according to local regulations. Fulvestrant will be supplied as two 5-mL clear neutral glass barrels, each containing 250 mg/5 mL of fulvestrant solution for intramuscular injection and fitted with a tamper evident closure. The solution for injection is a clear, colorless to yellow, viscous liquid.

Fulvestrant should be stored at refrigerated (2-8 °C). It should be stored protected from light and in the original packaging until the time of use.

# 5.3.2. Fulvestrant Dosage and Administration

The approved dose of fulvestrant is 500 mg administered intramuscularly into the buttocks. The injection should be as two 5 mL injections and should be administered slowly (1-2 minutes per injection). Injections should be given on days 1 and 15 of Cycle 1, and on day 1 of each subsequent 28 day cycle.

Technique for administration of the injection is outlined in the package insert. Because fulvestrant is administered intramuscularly, it should be used with caution in patients with bleeding diatheses, thrombocytopenia, or anticoagulant use.

#### 5.3.3. Fulvestrant Dose Modifications

In the event that an Investigator believes a dose modification is required for fulvestrant, the Sponsor and Medical Monitor should be contacted. The Investigator should use the local package insert for current dose modification guidelines for fulvestrant.

#### 5.3.4. Potential Toxicities with Fulvestrant

Because fulvestrant is given intramuscularly, it is should be used with caution in patients with bleeding diatheses, thrombocytopenia, or anticoagulant use.

Investigators should refer to the current fulvestrant package insert for information regarding potential interactions and toxicities.

In a clinical trial of fulvestrant given at 500 mg in advanced breast cancer as described in the current US fulvestrant package insert (AstraZeneca, 2012), the most frequently reported adverse events include: injection site pain (11.6%), nausea (9.7%), and bone pain (9.4%). Additional adverse events reported in  $\geq$ 5% of patients include: arthralgia (8.0%), headache (7.8%), back

pain (7.5%), fatigue (7.5%), extremity pain (6.9%), hot flashes (6.6%), vomiting (6.1%), anorexia (6.1%), asthenia (5.8%), musculoskeletal pain (5.5%), cough (5.3%), and constipation (5.0%).

Safety information for fulvestrant can be updated at any time by the original manufacturer. Merrimack Pharmaceuticals does not own rights to or make updates to the overall safety information distributed for fulvestrant. For this reason, Investigators should refer to the most current package insert for fulvestrant for any changes in safety information.

#### 5.4. Rules for Dose Omissions and Modified Treatment Schedules

It is intended that seribantumab and fulvestrant dosing occur on schedule per the protocol. In the event that dosing of any study drug has been held for 28 consecutive days and the investigator does not wish to continue dosing, the patient should be discontinued from treatment.

Dose modifications of seribantumab are not allowed. Any dose modifications to fulvestrant should be performed in line with the local package insert, and should be discussed and approved by the Sponsor prior to implementation.

# 5.5. Concomitant and Prohibited Therapies

All intercurrent medical conditions and complications of the underlying malignancy will be treated at the discretion of the investigator according to acceptable local standards of medical care. Patients should receive analgesics, antiemetics, antibiotics, anti-pyretics, GCSF, peg-GCSF, and blood products as necessary. All concomitant medications, including transfusions of blood products, will be recorded on the appropriate page of the case report form. Concomitant therapy (non-investigational products) includes any prescription medication, over-the-counter preparation, herbal therapy, or radiotherapy used by a patient between the 28 days preceding randomization and the study treatment discontinuation visit. After the End of Treatment Visit, only anti-cancer therapies will be collected.

The following therapies are not permitted while on study treatment:

- Other anti-neoplastic therapy, including cytotoxics, targeted agents, endocrine therapy or other antibodies (patients who have been on GnRH analogues for more than 90 days prior to study entry may continue on these while on study)
- Radiotherapy (patients who require a short course of palliative radiotherapy may continue on the study treatment after discussion between the investigator and sponsor)
- Any other investigational therapy

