on the date of randomization. Patients starting a new anti-cancer treatment prior to documented PD will be censored at the date of the last observed tumor assessment prior to start of the new treatment. Patients with documented PD or death after an unacceptable long interval (i.e., 2 or more missed or indeterminate scheduled assessments) will be censored at the time of the last observed tumor assessment date. PFS will be calculated as the date of the event/censor minus date of randomization plus one.

The primary analysis will be performed using a stratified log-rank test comparing the PFS difference between two treatment arms. The final PFS analysis will preserve the 1-sided alpha at 0.10. Stratification factors will include bone-only disease (yes, no) and geographic status (US, and non-US). Kaplan-Meier estimates will be used to display PFS time graphically. Cox proportional hazards model will be used to estimate hazard ratio and the corresponding 80% confidence interval. Median PFS event times and 80% confidence interval will be computed as well.

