### 4.2. Exclusion Criteria

Patients must meet all the inclusion criteria listed above and none of the following exclusion criteria:

- a) Prior treatment with an anti-ErbB3 antibody
- b) Prior treatment with a chemotherapy in the locally advanced or metastatic disease setting
- c) Patients cannot have received prior treatment with fulvestrant or other SERDs in the locally advanced or metastatic setting
- d) Uncontrolled CNS disease or presence of leptomeningeal disease
- e) Inflammatory breast cancer
- f) History of another active malignancy that required systemic therapy in the last 2 years. Patients with prior history of in-situ cancer or basal or squamous cell skin cancer are eligible
- g) Active infection, or an unexplained fever > 38.5°C during screening visits or on the first scheduled day of dosing, which in the investigator's opinion might compromise the patient's participation in the trial or affect the study outcome. At the discretion of the investigator, patients with tumor fever may be enrolled
- h) Known hypersensitivity to any of the components of seribantumab, fulvestrant, or who have had hypersensitivity reactions to fully human monoclonal antibodies
- i) Received other recent antitumor therapy including:
  - Investigational therapy administered within the 28 days or 5 half-lives, whichever is shorter, prior to the first scheduled day of dosing in this study
  - Radiation or other standard systemic therapy within 14 days prior to the first scheduled dose in this study, including, in addition (if necessary), the timeframe for resolution of any actual or anticipated toxicities from such radiation
- i) NYHA Class III or IV congestive heart failure
- k) Patients with a significant history of cardiac disease (i.e. uncontrolled blood pressure, unstable angina, myocardial infarction within 1 year or ventricular arrhythmias requiring medication) are also excluded

- 1) Uncontrolled infection requiring IV antibiotics, antivirals, or antifungals; or active human immunodeficiency virus (HIV) infection, active hepatitis B infection or active hepatitis C infection
- m) Any other medical condition deemed by the Investigator to be likely to interfere with a patient's ability to sign informed consent, interfere with a patient's ability to cooperate and participate in the study, or interfere with the interpretation of the results

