- A new anti-cancer treatment is started prior to documented progression and ≤ 30 days after treatment discontinuation, then censorship is at the date of the last tumor assessment that verified lack of disease progression prior to the new treatment
- Patients with documentation of progression or death after an unacceptably long interval (i.e., 2 or more consecutively missed or indeterminate/not evaluable assessments) since the last tumor assessment will be censored at the date of last tumor assessment documenting no progression

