#### Target disease

- Complete Response (CR): Complete disappearance of all target lesions with the exception of nodal disease. All target nodes must decrease to normal size (short axis < 10 mm). All target lesions must be assessed.
- Partial Response (PR): Greater than or equal to 30% decrease under baseline of the sum of diameters of all target measurable lesions. The short diameter is used in the sum for target nodes, while the longest diameter is used in the sum for all other target lesions. All target lesions must be assessed.
- Stable: Does not qualify for CR, PR or Progression. All target lesions must be assessed. Stable can follow PR only in the rare case that the sum increases by less than 20% from the nadir, but enough that a previously documented 30% decrease no longer holds.
- Documented Progression Disease (PD): 20% increase in the sum of diameters of target measurable lesions above the smallest sum observed (over baseline if no decrease in the sum is observed during therapy), with a minimum absolute increase of 5 mm.
- Not Evaluable: Progression has not been documented, and
  - $\circ$  one or more measurable target lesions have not been assessed
  - o or assessment methods used were inconsistent with those used at baseline
  - or one or more target lesions cannot be measured accurately (e.g., poorly visible unless due to being too small to measure)
  - o or one or more target lesions were excised or irradiated and have not reappeared or increased

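### Permitted palliative radiotherapy to a target lesion can make performed scans count as missed, so a later observed progression or death is censored; the PFS rules need an exception and one stated handling

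*Protocol*

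**What the plan says.** **Radiotherapy on study.** Protocol section 5.5 lists radiotherapy among therapies not permitted on study treatment, with one exception: "patients who require a short course of palliative radiotherapy may continue on the study treatment", after discussion between investigator and sponsor. Section 7.7 keeps scans at 8-week intervals until investigator-assessed progression, whatever the treatment schedule.

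**Evaluability.** In the SAP appendix, target response is not evaluable if progression has not been documented and a listed condition holds. One condition is "or one or more target lesions were excised or irradiated and have not reappeared or increased". In Table 1 of the appendix, a not evaluable target response with no non-target progression and no new lesion gives an overall status of not evaluable.

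**Gap rule.** SAP section 3.1 censors progression or death after "2 or more consecutively missed or indeterminate/not evaluable assessments" at the last assessment documenting no progression, and Table 3.1 repeats this. The protocol synopsis has a similar rule for missed or indeterminate scheduled assessments.

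**New treatment.** The synopsis states: "Patients starting a new anti-cancer treatment prior to documented PD will be censored at the date of the last observed tumor assessment" before that treatment began. The SAP version is narrower: "A new anti-cancer treatment is started prior to documented progression and ≤ 30 days after treatment discontinuation". Neither document defines the term or mentions palliative radiotherapy in this context.

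**The concern.** A patient given a permitted short course remains on randomised treatment and continues to be scanned. Her follow-up has no gap, yet the rule written for gaps can apply to her. Whether her progression counts then depends on how long she stayed free of progression after radiotherapy: early progressions are kept and later ones discarded. That is the wrong outcome for the primary endpoint, because the progression or death was observed and dated.

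Need for palliative radiotherapy may also mark worsening disease, so censoring linked to it could be informative. The undefined term adds a second problem: two analysts could classify the same patient differently under the synopsis rule.

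**Working it through.** **1. The plan's own figure.** Inputs from protocol section 10.2: hazard ratio 0.57, one-sided alpha 0.10, power 80%, 1:1 allocation. Schoenfeld formula: d = 4(z₀.₉₀ + z₀.₈₀)² / (ln HR)² = 4(1.2816 + 0.8416)² / (0.5621)² = 57.1, rounded up to 58. Power at 58 events is Φ(√58/2 × 0.5621 − 1.2816) = 80.5%. The stated 58 is reproduced.

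**2. One patient through the rules.** Suppose an evaluable week 8 scan without progression, radiotherapy to a target lesion at week 10, no regrowth, and then progression by a new lesion.

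| Progression first seen | Not evaluable scans before it | PFS outcome under the SAP |
|---|---|---|
| Week 16 | 0 | Event at week 16 |
| Week 24 | 1 (week 16) | Event at week 24 |
| Week 32 | 2 (weeks 16, 24) | Censored at week 8 |

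A death after two such scans is censored in the same way. The return to week 8 is explicit in the SAP, which uses the last assessment documenting no progression. The synopsis says the last observed assessment and does not say whether a performed but indeterminate scan qualifies.

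**3. Limits of this path.**
- Not evaluable applies only while progression is undocumented. A new lesion, non-target progression, or regrowth of the irradiated lesion can still establish progression.
- Irradiating a non-target lesion does not trigger it: Table 1 of the appendix keeps stable disease or partial response when the non-target response is not evaluable. Bone disease without a measurable soft-tissue component is non-measurable, hence non-target.
- The irradiated-lesion text is in a SAP that names protocol 02-03-10, a phase 3 trial of exemestane or fulvestrant with 195 events. This protocol is MM-121-02-02-10. On its own, it cites RECIST v1.1 and counts indeterminate scans, without saying what irradiation does.

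**4. Is permitted radiotherapy a new anti-cancer treatment?**
- Towards yes: the synopsis rule is not confined to patients off treatment, and exclusion criterion i lists radiation under "Received other recent antitumor therapy including".
- Towards no: section 5.5 counts as concomitant therapy "herbal therapy, or radiotherapy used by a patient between the 28 days preceding randomization and the study treatment discontinuation visit", and gives radiotherapy a separate bullet from "Other anti-neoplastic therapy, including cytotoxics, targeted agents, endocrine therapy or other antibodies". The SAP rule is tied to treatment discontinuation, and Table 3.1 counts documented progression on treatment as an event.

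**5. Size.** The documents give no radiotherapy rate, so all rates below are assumptions. Simulation: 1,500 trials per scenario, 40 patients per arm, exponential PFS with medians 4 and 7 months, uniform accrual over 16 months, progression dated at the next 56-day scan, unstratified log-rank test at one-sided 0.10, and cut-off at 58 counted events. Every course is taken to hit a target lesion, which overstates the not-evaluable effect. Monte Carlo error is about √(0.8 × 0.2/1500) = 1 percentage point.

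- *Not-evaluable rule, radiotherapy unrelated to prognosis and equal in both arms.* At 10%, power is 78.7% with all progressions counted and 78.7% under the rule; mean cut-off moves from month 20.1 to 20.7. At 20%, power is 79.3% and 80.9%; cut-off moves to month 21.6. Over assumed rates of 5% to 20%, including the late, unequal scenarios below, the delay is about 0.2 to 1.5 months.
- *Not-evaluable rule, radiotherapy late and unequal* (second half of the time to progression; 10% control v 5% seribantumab, or 20% v 10%). There is no loss of power, and the Cox hazard ratio changes by 0.004 or less.
- *Synopsis read to include radiotherapy, same late and unequal use.* Power falls from about 78–79% to 74–76% (10% v 5%) and from about 80% to 70–71% (20% v 10%). The Cox hazard ratio moves from about 0.57 to about 0.60–0.61.

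**6. If the cut-off were fixed instead.** Expected events per arm at month T are n[1 − (e^(−λ(T−16)) − e^(−λT))/(16λ)], with λ = ln 2/median. At T = 20 this gives 33.2 + 26.5 = 59.7. The margin over 58 is 1.7, or 2.9%. Starting from 58 events, losing 5% of progressions leaves 55.1 and 79.0% power; losing 10% leaves 52.2 and 77.3%. These are assumed shares of progressions lost, not radiotherapy rates.

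**The case against.** The strongest counter-argument is that the documents mostly leave a term undefined. Section 5.5, which governs on-study use, treats radiotherapy as concomitant. Exclusion criterion i is a pre-study washout rule. The SAP new-treatment rule does not reach a patient still on treatment. The not-evaluable path needs an irradiated target lesion, no regrowth, two consecutive not evaluable scans, no earlier progression elsewhere, and a SAP that names another protocol. Section 7.7 calls for an unscheduled scan when progression is suspected, so worsening that prompts radiotherapy may often be dated as progression first. Censoring detail is deferred to the SAP, which need only be complete before database lock.

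Most of this stands, and it rules out two stronger readings. A reader might infer that every patient given permitted radiotherapy is censored as having started new therapy; the text in step 4 does not support that. A reader might also infer that the trial loses events and power. But the synopsis starts the primary analysis when 58 PFS events have occurred, and censored patients are not events, so the cut-off moves instead.

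What does not fall away is the not-evaluable path: it is written, it has no exception for radiotherapy that the protocol permits, and it discards an observed event. The planned sensitivity analyses do not answer it. Protocol section 10.5.2 turns all censored patients into events; SAP section 5.5.2 does so for the seribantumab arm only, at the censoring date. Neither isolates radiotherapy or restores the true progression date.

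**Conclusion.** The point holds in a limited form. If this SAP governs the trial, its text, together with the gap rule in both documents, censors an observed progression or death after two or more scans that were performed but are not evaluable because a target lesion was irradiated. Separately, the status of permitted radiotherapy under the synopsis new-treatment rule is unstated. Section 5.5 and the SAP suggest that it is not new treatment, but the passages must be reconciled.

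The numerical effect of the not-evaluable rule is small: a later cut-off by about 0.2 to 1.5 months at assumed rates of 5% to 20%, with no visible loss of power and almost no change in the hazard ratio. In the scenarios examined, with the cut-off at 58 counted events, lost power and a shifted hazard ratio appear only if the synopsis is read to include radiotherapy and its use is late and unequal between arms. The documents neither state nor exclude such use. The case for changing the rule is that it gives an individual patient the wrong primary outcome and that correcting it is cheap.

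**What to change.** Change only the PFS rules (protocol synopsis and section 10.5.1; SAP section 3.1 and Table 3.1). Leave section 5.5 unchanged.

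1. State that a performed scan that is not evaluable solely because a target lesion was irradiated does not count towards the rule on two or more missed or indeterminate assessments. Later documented progression or death is then an event on its own date.
2. Align the synopsis with the SAP so that radiotherapy permitted under section 5.5 during continued randomised treatment is handled in one stated way for PFS. Specify the other handling as a sensitivity analysis.
3. Confirm which SAP governs this trial and carry the same wording into it.

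The cost is a few sentences and one extra analysis, settled before database lock. Radiotherapy is already recorded as concomitant therapy; applying item 1 also requires knowing whether the irradiated lesion was a target lesion. Protocol section 10 asks for an amendment if a change to the primary analysis is major, so the synopsis wording should be updated together with the SAP. The small downside is that PFS after radiotherapy rests on fewer target lesions.
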